The study will last a duration of about an hour, and take place on a single day. It will be conducted in a lab room of the PI, which is isolated from others in the space. We will recruit 30 participants. We hope to recruit people who show no tension in the upper back, others with moderate tension, and yet others tension to a greater degree. We will assign participants to a group based on the screening question, administered via Qualtrics, which will be asked of them upon their response to our email advertisement. We are attempting to screen so as to attain a balance in number of participants between the groups. Once a participant is selected to participate, we will invite them and have them sign the consent form. After this, they will complete a demographic questionnaire, administered verbally. Then, they will change into the clothing (e.g., sports bra, halter top, or swimming suit, etc.) that they were asked to bring in order to expose their upper back/neck region. This will take place in a separate, isolated room within the laboratory space, and we will provide them also with a gown for added privacy. Two researchers will be in the room during the session, with the gender of the researchers taken into account per participant. For example, for a male participant, we plan to have a male researcher present during the session along with the female physical therapist. For a female participant, we plan to have both the female physical therapist and a female researcher present. Next, the actual study procedures include that the proctors will apply a non-toxic, washable ink to the skin of the participant's upper back, in a square about 10 by 10 centimeters. This is easily washed off at the study's conclusion. Once the ink is applied, we will ask the participant to lie down on a massage table. An experienced, trained, and licensed physical therapist will perform an assessment manually, where they will compress their fingers into the skin, as well as

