Title: Optical Measurements of the Skin Surface to Infer Distinctions in Myofascial Tissue Stiffness

NCT number: NCT06390085

Date: February 3rd, 2023

Statistical Design and Power

Aim 1. We will evaluate the sensitivity of a suite of mechanical biomarkers. Using the imaging approach, we will create an optimal set of biomarkers which is the best classifier of myofascial pain state. In order to select the best suite of complementary metrics, which are most effective in predicting pain state, and which are simplest to accurate we will develop a classification strategy, we will perform multi-dimensional cluster analysis based on measured biomarkers. By using the biomarkers as predictors, data points representing different stimulus sets will be clustered into certain distinct groups based on the minimized average deviation (Jenks natural breaks classification method, 1-dimensional) and the minimized distance to the centroid (k-Means clustering, 2,3-dimensional). The match rate between clustered groups and ground-truth stimulus sets will determine the utility of unique biomarkers.

Aim 2. We will refine the requirements of the imaging deployment by evaluating tradeoffs in the array of ink speckles on the skin, in particular their density and heterogeneity requirements, to determine to what extent the density can be reduced yet still achieve similar imaging accuracy. We will perform ANOVA and t-tests with p values set at 0.5.

Sample size justification and power. Aim 1 will enroll 15 individuals. We will have a >80% power to identify biomarkers that have a moderate/strong rank correlation (e.g., Spearman's correlation ≥ 0.57) with pain. Aim 2 will enroll 6 individuals. These participants will be evaluated in refining requirements for imaging deployment, data collection, and data analysis.

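### Aim 1 seeks a classifier of pain state, but its only selection rule scores clusters against stimulus sets, a label that neither document defines or links to pain

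*SAP*

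**What the plan says.** The SAP (Statistical Design and Power, Aim 1) states the goal as "we will create an optimal set of biomarkers which is the best classifier of myofascial pain state" and wants the metrics "which are most effective in predicting pain state".

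The operative sentences use a different label. In the clustering step, "data points representing different stimulus sets will be clustered into certain distinct groups", by Jenks natural breaks in one dimension and k-means in two or three. The scoring step is: "The match rate between clustered groups and ground-truth stimulus sets will determine the utility of unique biomarkers". No other selection rule is given.

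Pain appears in two other places:
- The SAP's sample size paragraph says "Aim 1 will enroll 15 individuals" and "We will have a >80% power to identify biomarkers that have a moderate/strong rank correlation" of at least 0.57 with pain.
- The protocol (Data Sources, pain assessment) plans to relate rated pain, taken on both sides before and after massage, to the observed deformation.

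On what is applied to the skin, the protocol's Study Overview has the therapist "perform an assessment manually, where they will compress their fingers into the skin, as well as" stretch it laterally, on both sides, before and after the massage. The pain categories have their own names in the protocol's Participant Groups section: Active, Latent and Normal.

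**The concern.** Jenks and k-means are unsupervised, so no outcome shapes the clusters. The reference label enters Aim 1 only through the match rate, and whatever that label is decides which biomarkers are chosen. The label written is stimulus sets, and it stands in both operative sentences.

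In its plain sense the term means the manual condition applied. The protocol describes the same assessment for all participants, whatever their pain group. A good match to it would show that a biomarker tells one manual condition from another, which is not evidence about pain. The resulting set could still be reported as a pain-state classifier. The protocol says the work is meant to support a later grant application, so such an error would carry forward.

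**Working it through.** **1. The plan's own figure.** The SAP gives no expected match rate, threshold or number of clusters, so there is nothing to reproduce for the rule itself. The one Aim 1 figure is power above 80% for a Spearman correlation of 0.57 with n = 15; no significance level is stated for Aim 1. By Fisher's z, atanh(0.57) × √(15 − 3) = 0.6475 × 3.464 = 2.243. At two-sided 0.05, power = Φ(2.243 − 1.960) = 0.61. At one-sided 0.10 it is Φ(2.243 − 1.282) = 0.83. That is a separate matter. What counts here is that the power statement concerns correlation with pain, while the selection rule concerns match to stimulus sets.

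**2. The three statements side by side.**

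| Element of Aim 1 | Quantity named |
|---|---|
| Goal | pain state |
| Selection rule | stimulus sets |
| Power basis | rank correlation with pain |

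No sentence in either document joins the second row to the others.

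**3. Illustration: assumptions.** The documents give no effect sizes, so these are mine:
- one compression and one stretch value per person, pooled;
- three equal pain groups;
- normal biomarkers with SD 1;
- two-class Jenks, with clusters matched to labels by the best alignment.

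N = 15 is the SAP's Aim 1 number and N = 30 the total in the protocol's Study Overview. Biomarker A differs between the two actions by d = 1 to 4 SD and has no pain signal. Biomarker B differs by 1.5 to 3 SD per pain step and is the same under both actions.

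**4. Scored against stimulus.**
- *A.* A midpoint cut gives a match of Φ(d/2): Φ(0.5) = 69% at d = 1 and Φ(2) = 98% at d = 4. Simulation at N = 15 agrees (69-98%).
- *B.* If both values from one person fall in the same cluster, exactly one of them matches, so B is pulled towards 50%. Simulation at N = 15 gives 53-55%.
- *Pure noise.* Best alignment lifts noise above 50%. With M points and equal halves, the count in one cell has variance (M/2)(1/4)(M/2)/(M − 1). For M = 30 this is 1.94 (SD 1.393), so the match rate has SD 2 × 1.393/30 = 0.093 and expectation about 0.5 + 0.798 × 0.093 = 57%. For M = 60 the variance is 3.81 (SD 1.953), the match rate has SD 0.065, and the expectation is about 55%. Simulation gives 57% and 55%.

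A scores above B in 90-100% of simulated studies at N = 15 and in 98-100% at N = 30. B scores slightly below noise.

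**5. Scored against pain state within one action.** At N = 15 the order reverses: B matches 69% to just under 90%, while A scores 50%, which is the noise level for three classes and 15 points.

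**6. A second layout.** Take three stimulus sets, three pain groups of 5, and 45 points. A stimulus-only biomarker with steps of d SD should match (4Φ(d/2) − 1)/3.
- At d = 3 this is (4 × 0.9332 − 1)/3 = 91%; simulated 90.5%, against 37.8% when scored on pain.
- At d = 6 it is (4 × 0.99865 − 1)/3 = 99.8%; simulated 99.8%, against 33.5% on pain.
- A pain-only biomarker at 6 SD gives the mirror image: 33.5% on stimulus and 99.9% on pain.
- Noise gives about 43% on either label.

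**The case against.** The strongest reply is that stimulus sets is undefined, and that the authors may have meant the pain groups. The clustering is introduced as the way to find metrics that predict pain state, so the ground truth could be pain state under a poor name. Left versus right side, or before versus after massage, are also possible readings. This stands as far as intent goes: the documents do not establish that the rule compares compression with stretch. But no passage gives the term a pain meaning, and if one was intended the same edit is needed.

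A reader might infer that pain plays no part in judging biomarkers at all. The documents do not support that. The power statement and the protocol's planned association both bring pain in, and a biomarker without pain information should show no correlation there. What is missing is any link from those analyses to selection.

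The illustration also has limits. It pools values across actions, which no passage plans. The protocol's summary speaks of biomarkers based on lateral mobility, compression and distraction, which suggests metrics tied to one action. If so, clusters that merely separate compression from stretch would not arise. The biomarkers were built to carry one signal each, so the ranking follows from the construction.

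Two stronger statistical readings also fail. One is that the rule produces false positives under a global null: B carries a real pain effect, so no such null was simulated. The other is that B at 53-55% is a little above chance: 50% is not the chance level under best alignment.

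**Conclusion.** The concern holds in a limited form. Aim 1's goal is pain state, while its only stated selection rule scores against a label that neither document defines or connects to pain. On the plain reading, the rule does not use pain and can place an uninformative biomarker first. Both documents leave the pain analyses unattached to selection.

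That the label decides selection follows from the text and from the unsupervised methods; it does not depend on sample size or on the power figure. The percentages do depend on assumed effect sizes, on pooling across actions and on the number of classes. They show that misranking is possible and can be large, not how often it would occur in this study. Because this is the one rule that chooses the biomarkers, it should be settled before analysis.

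**What to change.** 1. In both Aim 1 sentences, replace stimulus sets with pain state as the ground-truth label. Use the Active, Latent or Normal group if the unit is the participant. If the unit is the side, use rated pain, with the categories fixed in advance, and do not treat the two sides of one person as independent.
2. If values from different manual actions would otherwise be pooled, cluster and score within one action at a time.
3. Compare each match rate with a permutation reference, shuffling labels in a way that respects the unit of analysis, instead of with 50%.
4. Say how the Spearman correlation with pain enters selection, or that it does not.
5. Report any match to the applied stimulus only as a technical check of the imaging, with no part in choosing biomarkers.

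The cost is a rewording of two sentences, a few added lines and a simple permutation run. The groups and bilateral pain ratings are already planned, so no new data are needed. The SAP does not currently name the three groups, so it must take their definitions from the protocol. Reported match rates will probably be lower, since pain state is likely to be harder to separate than type of manual action.

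### SAP Aim 2 sets its test threshold at 0.5 and has no rule that could show that a sparser speckle array is similarly accurate

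*SAP*

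**What the plan says.** The SAP describes Aim 2 as "evaluating tradeoffs in the array of ink speckles on the skin, in particular their density and heterogeneity requirements", and gives its purpose as "to determine to what extent the density can be reduced yet still achieve similar imaging accuracy". The whole analysis is one sentence: "We will perform ANOVA and t-tests with p values set at 0.5".

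The sample size section adds "Aim 2 will enroll 6 individuals" and "These participants will be evaluated in refining requirements for imaging deployment, data collection, and data analysis". For Aim 2 it gives no power, effect size, standard deviation or tolerance.

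No other significance level can be found. The Aim 1 statement, "We will have a >80% power to identify biomarkers that have a moderate/strong rank correlation", gives no alpha. The protocol contains no test threshold and no comparison of speckle densities. Its Study Overview describes ink applied to the "upper back, in a square about 10 by 10 centimeters", that is, one inked area per person.

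**The concern.** There are two linked problems.

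1. **The threshold.** A test at 0.5 is close to uninformative as evidence of a difference, because arrays that perform equally would be declared different as often as not.
2. **The question and the test do not match.** Aim 2 needs evidence that a sparser array is good enough. ANOVA and t-tests can give evidence that arrays differ. Failing to find a difference, above all in 6 people, may mean that the arrays are alike or only that the measurement was too imprecise to tell.

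What is at stake is the density and heterogeneity requirement that Aim 2 is meant to set for later deployment of the imaging system. The problems belong together because correcting only the first worsens the second: a stricter test is non-significant more often, so reading non-significance as similarity would accept more degraded arrays.

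**Working it through.** **Inputs from the SAP.** Threshold 0.5; tests ANOVA and t-tests; n = 6. The threshold is a chosen value and Aim 2 states no derived figure, so there is nothing of the plan's own to reproduce first.

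**Assumptions.** Neither document states Aim 2's layout, sidedness or number of comparisons. Tests are taken as two-sided, and two layouts are shown:
- *Paired*: each of 6 people gives one difference between two densities. Unit: SD of that difference; df = 5; standard error 1/√6 = 0.408 SD.
- *3 versus 3*: each person has one density. Unit: between-person SD; df = 4; standard error √(1/3 + 1/3) = 0.816 SD.

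The two SDs are different units and should not be compared with each other.

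**Step 1: false differences.** With no true difference, a valid p-value is uniform, so P(p < 0.5) = 0.50 whatever the n, SD or layout. Simulation agrees: 0.499 for the paired and 0.499 for the 3-versus-3 layout, and 0.500 for repeated-measures ANOVA in 6 people with 3 or 4 levels. At 0.05 the rate is 5%. The number of tests is not given. If k tests were independent, the chance of at least one false difference at 0.5 would be 1 − 0.5^k: 75% for k = 2 and 87.5% for k = 3.

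**Step 2: what changing 0.5 to 0.05 does to power.** Noncentral t, true difference 1 SD, noncentrality = 1/standard error:

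| Layout | Noncentrality | Critical t at 0.5 | Power at 0.5 | Critical t at 0.05 | Power at 0.05 |
|---|---|---|---|---|---|
| Paired, df 5 | 2.449 | 0.727 | 0.958 | 2.571 | 0.507 |
| 3 versus 3, df 4 | 1.225 | 0.741 | 0.727 | 2.776 | 0.159 |

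In the paired layout a true 1-SD difference is missed 4% of the time at 0.5 and 49% at 0.05. A 0.5-SD difference is missed 27% and 83% of the time. Non-significance therefore does not establish similarity at either threshold.

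**Step 3: what a similarity rule could show.** Two one-sided tests (TOST), each at 0.05, amount to asking that the 90% confidence interval lie inside ± the margin. The half-width at the true SD is t(0.95, df) × standard error: 2.015 × 0.408 = 0.82 SD paired, and 2.132 × 0.816 = 1.74 SD for 3 versus 3. Power when the true difference is zero:

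| Margin | Paired | 3 versus 3 |
|---|---|---|
| 1.0 SD | 0.41 | 0.03 |
| 1.4 SD | 0.80 | 0.12 |
| 2.0 SD | – | 0.38 |
| 2.92 SD | – | 0.80 |

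If only a loss of accuracy matters, a one-sided 95% bound reaches 80% power at a margin of 1.19 SD paired, or 2.48 SD for 3 versus 3.

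**Step 4: can Aim 1 reveal the intended alpha?** It does not point to 0.05. With 15 people and a Spearman correlation of 0.57, two-sided 0.05 gives 55–61% power depending on the variance formula, not above 80%. That shortfall is a separate matter. Here it means only that the Aim 1 statement cannot be used to confirm the Aim 2 threshold.

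**The case against.** The strongest reply is that 0.5 is a plain misprint, so the 50% rate is arithmetic on a printed digit and not an error rate anyone expects to see. That is likely, and it limits the practical harm of the first problem. But the sentence is the operative analysis rule, and no other text lets a reader correct it.

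The direction of the error also matters. Calling equal arrays different pushes towards keeping a denser array, which does not harm accuracy. The harmful error is a false claim of similarity, and the correction to 0.05 makes that more likely. This stands. It softens the first problem and strengthens the second.

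It can also be said that Aim 2 is exploratory refinement in 6 people, where a formal equivalence rule may be more than is needed. That is fair: estimates with confidence intervals and no similarity claim would be an acceptable plan. What is not workable is to name formal tests that cannot answer the question.

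Finally, the two layouts do not exhaust the possibilities. The protocol describes assessment on both sides, repeated after the massage, with three cameras, and sparser arrays might conceivably be derived from the same video. With no SD or accuracy measure given, six people could be enough if technical variation is small against the tolerance. This also stands: the figures in SD units are illustrations. It does not affect the 50% result or the absence of a rule.

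**Conclusion.** The concern holds on both parts, and the threshold must be fixed. At 0.5 as written, each test of equally accurate arrays declares a difference 50% of the time; this rests on no assumption beyond a valid test. That 0.05 was intended is probable but unconfirmed.

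The absence of an accuracy measure, tolerance and decision rule means that Aim 2 cannot support a statement of similar accuracy at any threshold. How much 6 people could show depends on the unstated layout. A similarity rule has 80% power only for a margin of about 1.4 SD of the paired differences, or about 2.9 between-person SDs if the six are split. These cannot be turned into engineering units from the documents.

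**What to change.** **Required.** Confirm the intended alpha and sidedness and correct the figure (conventionally 0.05, two-sided).

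**In the same edit**, because the number alone leaves Aim 2 unanswered:
- State the layout: whether each person contributes several densities or one.
- Name the accuracy measure and a tolerance in its own units, fixed before the results are seen.
- Call a reduced density similar only if the 90% confidence interval of its difference from full density lies inside the tolerance. If only loss matters, use the one-sided bound. Otherwise report estimates with intervals and make no similarity claim.

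**Optional.** Testing densities in a fixed order from densest to sparsest controls the error for density on a single accuracy measure. Heterogeneity needs its own rule, and the SAP should say whether the two share one error rate.

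**Cost.** One number, a few sentences and agreement on a tolerance. The edit itself needs no new data. The drawback is that a tight tolerance may not be demonstrable with 6 people, especially if each has only one density. If density and heterogeneity split the error rate equally (95% intervals), paired power falls from 0.41 to 0.22 at a 1.0-SD margin and from 0.80 to 0.60 at 1.4 SD. Aim 2 may then have to report estimates with intervals only.

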stretch the skin laterally. The assessment is not anticipated to cause any pain to the skin. We will ask the participant to self-reported pain level using the questions from the study assessment. With a set of off-the-shelf cameras above the participant's back, we will record the movements of the fingers of the clinician as well as the participant's skin movements. The reason we use the ink is that it makes it easier for us to track the skin movements in high-resolution video. We will not record audio, and we will not record any images of any part of the participant other than the area defined in ink on the back. Once the clinician performs this assessment, on both left and right sides, she/he will perform a soft tissue massage intervention where she/he will use moderate massaging and compression. Following this intervention, we will perform a final assessment manually, as done when the study began. The cameras will send data to a laptop which then uploads data to a UVA Sharepoint server. Risk are minor and include that perhaps someone's skin could be irritated by the washable ink or the soap when washing it off. The participants would be compensated with a \$25 gift card.

Is this study topic relevant to cancer risk factors, prevention, cancer treatment, or survivorship (e.g., pain, financial toxicity, etc.), or will the study purposefully include participants currently or previously diagnosed with cancer, or their caregivers?

No

(optional) Study Overview file upload: Below you have the option to upload additional files to help the Board better understand your study. You are not required to provide any additional explanation beyond completing the text boxes provided in this Study Overview section; however, for example, if you are using a new technology or a complicated process that would be more easily demonstrated with an image or video, you can upload the file here.

Participant Groups

Participant Group Name: Active

Age Range (years): 18-75

Vulnerable populations: no vulnerable population (none)

Maximum number of participants, in this group, expected to enroll over the life of the study: 15

Minimum number of participants, in this group, expected to enroll over the life of the study: 15

Total number of participants, in this group, ever enrolled: 0

Approximate number of participants, in this group, currently enrolled: 0

Future Enrollment: We will enroll participants, in this group, during the next twelve months

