Will a recording device (e.g. audio, video, photographic) be used to collect data/materials from participants? Yes

What type(s) of recording device(s) will be used in this data tool? Video

Describe each recording device(s) and provide a justification for using the recording device.

We need the imaging information to capture the deformation patterns of the skin surface of the participant relative to the movements of the clinician's fingers. This is video data, taken at 30 - 100 frames per second. The recording devices is a raspberry PI camera, and we use three of them, aimed at the same point, so as to acquire 3D data from slightly distinct angles, so as to reconstruct the skin surface accurately. The exact model is a monocular camera (12 MP, Raspberry Pi High Quality, UK) with wide angle lenses (6 mm Vilros, Lakewood, NJ, USA) connected to microcontrollers (Raspberry Pi Zero W boards, UK).

Are the participant's identifying information included as part of the data at any time? No

How will you receive the data so that the data are not linked to identifying information?

A number will be assigned to each participant, starting at 1 and following. This number will be added to the signed consent forms. These forms will be stored as noted above. Any data linking identifying information will be stored securely and separately from the imaging data.

Data Source Name: Verbal pre and post pain assessment

When will the data be collected? Data will be collected after IRB-SBS approval of this protocol.

Who will collect the data? Primary data source

Describe this Data Source.

Pain levels of the participant at the point of each manual assessment, i.e., before and after the massage intervention. These are to be taken bilaterally. We will associate this data with the imaging data to determine if the level of pain is associated with mechanical deformation cues we observe, e.g., amount of skin strain.

Will a recording device (e.g. audio, video, photographic) be used to collect data/materials from participants? No

Are the participant's identifying information included as part of the data at any time? No

How will you receive the data so that the data are not linked to identifying information?

We will obtain these verbally and store them in a spreadsheet using the numerical identifier for that patient, and stored in a file structure/directory of the same number.

Associate Data Sources with Data Sources

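### The SAP's >80% power at Spearman 0.57 does not follow from 15 people (about 59% at two-sided 0.05 with one pair each), and the sample size reads 15, 30 or 45

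*SAP*

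**What the plan says.** **SAP, Sample size justification and power.** The paragraph opens with this claim: "Aim 1 will enroll 15 individuals. We will have a >80% power to identify biomarkers that have a moderate/strong rank correlation", where the correlation is with pain and is given as "Spearman's correlation ≥ 0.57". The paragraph then adds "Aim 2 will enroll 6 individuals" without saying whether these six are among the 15 or additional to them. No significance level, sidedness or number of pairs per person accompanies the Aim 1 figure. The one level printed in the SAP is 0.5, and it is attached to Aim 2's ANOVA and t-tests.

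**Protocol, study overview.** "We will recruit 30 participants".

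**Protocol, Participant Groups.** The Active, Latent and Normal entries each carry "Minimum number of participants, in this group, expected to enroll over the life of the study: 15", with the maximum also 15. Each entry also expects 10 people over the coming year.

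**Protocol, Data Sources, verbal pain assessment.** Pain is recorded "before and after the massage intervention. These are to be taken bilaterally", so up to four pain readings per person exist.

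**The concern.** This is the only power statement in the two documents, and a correlation of 0.57 in 15 people looks too small for 80% power at a conventional level. If the plain reading is the intended one, a biomarker with a true correlation of 0.57 would be missed about 4 times in 10 at two-sided 0.05 (about 3 in 10 one-sided), where the SAP implies fewer than 2 in 10. A null result for a useful biomarker would then be easy to misread.

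The enrolment figures raise a second problem that needs no assumption: 30 people cannot fill three groups that each need at least 15.

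**Working it through.** **Inputs.** n = 15, power above 80% and Spearman 0.57 come from the SAP. Alpha, sidedness and one pair per person are assumptions, because the SAP does not state them.

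**Formula.** Power = Φ( atanh(ρ) / √(c/(n−3)) − z). Three variances are in use: c = 1 (plain Fisher z), c = 1.06 (Fieller, for Spearman) and c = 1 + ρ²/2 = 1.162 (Bonett-Wright).

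**Attempt to reproduce >80% at n = 15.** atanh(0.57) = 0.6475 and √12 = 3.464.

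- c = 1: 0.6475 × 3.464 = 2.243. Φ(2.243 − 1.960) = 0.611.
- c = 1.06: 2.243/√1.06 = 2.179. Φ(2.179 − 1.960) = 0.587.
- c = 1.162: 2.243/√1.162 = 2.080. Φ(2.080 − 1.960) = 0.548.

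Replacing 1.960 by 1.645 or 1.282 gives the one-sided rows. The simulation column uses bivariate normal data with population Spearman 0.57.

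| n = 15 | Fisher | Fieller | Bonett-Wright | Simulation |
|---|---|---|---|---|
| two-sided 0.05 | 0.611 | 0.587 | 0.548 | 0.59-0.60 |
| one-sided 0.05 | 0.725 | 0.703 | 0.668 | 0.71-0.72 |
| one-sided 0.10 | 0.832 | 0.815 | 0.788 | 0.83 |

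The SAP's figure is not reproduced at 0.05, one- or two-sided. The gap of about 20 points at two-sided 0.05 is well beyond the 6-point spread between formulas.

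**What 80% would need.** At two-sided 0.05, n = 3 + c × (2.8016/0.6475)², where 2.8016 = 1.960 + 0.8416. This gives 21.7, 22.8 and 24.8, so 22 to 25 people. With 15 people, the correlation detectable with 80% power is tanh(2.8016 × √(1.06/12)) = 0.68.

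**Other totals, two-sided 0.05.**

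| n | Fisher / Fieller / Bonett-Wright | Simulation | Detectable at 80% |
|---|---|---|---|
| 30 | 0.920 / 0.905 / 0.877 | 0.91 | about 0.50 |
| 45 | 0.987 / 0.983 / 0.973 | 0.99 | 0.41-0.42 |

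**Pooling several measurements from 15 people.** This was simulated with the same within-person correlation (ICC) in biomarker and pain, and with critical values taken under the clustered null at two-sided 0.05. The documents give no ICC, so a range is shown.

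| ICC | 0.3 | 0.5 | 0.65 | 0.7 | 0.8 | 0.9 |
|---|---|---|---|---|---|---|
| 2 sides | 89% | 85% | 80% | 79% | 74% | – |
| 4 measurements (sides × before/after, treated as exchangeable) | – | 96% | – | 88% | 81% | 73% |

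A cruder approximation for two sides, effective n = 30/(1 + ICC), is stricter: it needs an ICC of about 0.31 or less for 80%.

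**Counts.** 3 groups × 15 = 45 against 30 in the overview. The coming-year entries give 3 × 10 = 30.

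**The case against.** - **A figure that cannot be reproduced is not thereby wrong.** The 59% rests on inputs the SAP does not give. The protocol collects bilateral, before-and-after data, so one pair per person is not the only design it supports. With two sides and an ICC of 0.5, 15 people give 85%. This stands as a condition on the 59%. It does not rescue the claim, because the SAP states neither the pooling, nor the within-person correlation, nor a test that allows for it.
- **The 0.5 level.** At two-sided 0.5, 15 people would give 92-94%. That level belongs to Aim 2's tests and is probably a misprint, so it does not support the Aim 1 figure.
- **30 may be a one-year figure.** The coming-year entries sum exactly to 30, so 45 may be the life-of-study total. This is a plausible explanation, but the overview presents 30 as the study's recruitment, so the text still needs correcting.
- **15 may be a subset of a larger total.** The protocol does not mention aims, and the SAP (February 2023) predates the approval of the protocol's attachments (October 2023). On 30 or 45 people there is no power shortfall, which is a fair limit on the consequence. But the SAP ties its claim to 15, and neither document maps that 15 to a total.
- **The study is preliminary, and Aim 1 is scored by cluster match rate.** Both are true. The second adds a gap, since the power figure belongs to a correlation test that the Aim 1 analysis text does not describe.

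**Conclusion.** The concern holds. As written, >80% power for Spearman 0.57 in 15 individuals cannot be reproduced. With one pair per person it is about 59% at two-sided 0.05 (55-61%) and about 71% at one-sided 0.05 (67-73%). It reaches 80% only at a level near one-sided 0.10, or under a clustered analysis the SAP does not state. No adjustment is stated for testing a suite of biomarkers, and any such adjustment would lower these figures.

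The conflict between 30 people and three minimums of 15 is in the text itself and rests on no assumption.

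**What to change.** 1. State one total in both documents, make the three group minimums and maximums add up to it, and say whether Aim 1's 15 and Aim 2's 6 are subsets of it or additional.
2. For Aim 1, state alpha, sidedness and unit of analysis, and name the correlation test in the analysis text.
3. Restate the power to match. With one pair per person at two-sided 0.05:
   - Aim 1 at 15: about 59% power for 0.57, or 80% for about 0.68.
   - Aim 1 at 30: about 90% power for 0.57, or 80% for about 0.50, with the groups set to total 30.
   - If the group figures of 15 are the intended ones: change the overview to 45 and the SAP to match (about 98% for 0.57 if all 45 enter Aim 1).
4. If sides or time points are to be pooled, state the assumed within-person correlation and a test that accounts for clustering, and compute power for that test.

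**Cost.** Staying at 15 or 30 changes wording only, though at 15 with one pair per person the stated power becomes less favourable. Choosing 45 means 15 more participants than the overview states.
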